## 6 Study Procedures

All study procedures will take place at the Vanderbilt Psychiatric Hospital. We will recruit clinically stable outpatient adult men and women with schizophrenia or schizoaffective disorder, age 18-65, with similar clinical characteristics to those described in a previous clinical study of acute transdermal nicotine administration in subjects with schizophrenia and healthy controls. Inclusion and exclusion criteria are listed above in section 4. All participants will provide written informed consent. This study population, including non-smoking patients with schizophrenia, has been consistently successfully recruited for imaging studies in the lab of [name], in the quantities necessary for the current project.

#### 6.1 Baseline: day 0

Subjects completing a telephone or other initial screen will be invited to complete a baseline screening day in person. At this visit, a primary diagnosis of schizophrenia or schizoaffective disorder will be confirmed by clinical interview and/or the Structured Clinical Interview for DSM-V (SCID). A full screening interview will be performed to include medical, psychiatric, and substance use history, and mental status exam. Inclusion and exclusion criteria will again be fully reviewed with the potential subject. The consent documentation will be reviewed with the subject and all participants will provide written informed consent. Subjects will be monetarily compensated for their time spent in the initial screening visit regardless of their subsequent involvement in the study.

Similar to previous studies related to impulsive aggression in schizophrenia, at baseline subjects will be administered the Brief Psychiatric Rating Scale (BPRS), the Barratt Impulsiveness Scale to measure trait impulsivity, the short version of the UPPS-P (S-UPPS-P) to measure urgency and related impulsive constructs, the Buss-Perry Aggression Questionnaire to determine aggressive attitudes, and the Kaufman Brief Intelligence Test-2 (K-BIT-II). Subjects will provide urine samples to test for cotinine to confirm smoking abstinence, and they will also provide urine samples for urine pregnancy testing (if female) and toxicology. Electrocardiograms will be obtained as part of the screening medical evaluation. At the conclusion of the screening visit, if the

subject qualifies for the study and gives informed consent, the subject will be scheduled to return for day 1 of the study.

In some instances, the screening visit will be combined with the first testing session. This is to reduce the logistical burden for subjects for whom transportation may be difficult, as well as for individuals who may have difficulty getting time off from work. It is anticipated that this will reduce the number of subjects who drop out from the study without compromising subject safety.

#### 6.2 Testing: days 1 and 2

Testing occurs on two days separated by approximately one week, but no sooner than 5 days apart (Figure 1) to facilitate drug washout. Subjects will report to the Vanderbilt

Psychiatric Hospital. Female subjects will be administered a point of care urine pregnancy test to confirm absence of pregnancy. Subjects will have affixed to their skin a 7 mg nicotine patch or identical appearing placebo, covered by surgical tape so that neither the

subject nor the investigator can determine the identity. Previous studies of serum nicotine concentration suggests two hours post-patch application represents an approximate time of peak serum concentration in most subjects and is consistent with previously published protocols. Subjects will begin the behavioral task accompanied by EEG monitoring *at the latest* 120 minutes after patch placement, and will complete the task approximately 12 minutes later. At they time they will provide a saliva sample. This sample will be affixed solely with a non-identifiable code, frozen, and shipped to [name], University of Florida, for analysis of salivary nicotine which has been shown to correlate with serum nicotine levels and eliminates the need for venipuncture. The patch will then be removed.

interval. E, emotional block; NE, non-emotional block.

As noted above, up to two hours after nicotine or placebo patch placement, subjects will begin participation in an Emotional Go/NoGo task, based on the procedure described by Egashira et al, which compared medicated subjects with schizophrenia to healthy subjects and found the patient group was significantly more affected by negative emotional valence than were healthy controls despite only modest group differences with neutral valence stimuli. Subjects will also undergo electroencephalography during performance of the behavioral task. Fearful, sad, angry, and disgust faces (negative valence) and neutral faces will be taken from UPenn's publicly available PERT-96 color emotional stimuli bank. The entire task takes ~12 mins, including breaks, and is

performed in 5 blocks of 32 trials, with 3 emotional blocks with angry/fearful/sad/disgust faces and 2 non-emotional blocks (Figure 1). Each stimulus is presented for 1 s with a 1 s interstimulus interval. In each block the subject is instructed on the go/no-go targets, each comprising 50% of the task stimuli, with instructions changing at the halfway point in each block. Each block contains two instructions. For example: Emotional blocks: go-angry/nogo-fear or go-fear/nogo-angry; Non-emotional blocks: go-male/nogo-female or go-female/nogo-male (Figure 2). Error rates and reaction times are recorded.

Figure 2 Emotional Go/NoGo schematic. Subjects are given a target instruction at the start of each block for 6 seconds. There is 1 second of blank screen between each 1 second stimulus presentation. In this schematic, the subject would press a key ("Go") when presented with the first stimulus (angry; green border represents the correct response is "Go". This border would not be present in the actual task), and withhold pressing a key for the second stimulus (sad; red border).

Subjects will be monitored for at least 30 minutes after patch removal to confirm the absence of side effects that would compromise their safety upon leaving the hospital.

Subjects will return for day 2 of testing not less than 5 days following day 1. On day 2, subjects will receive the treatment they did not receive on day 1. They will be asked a series of standard questions to assess for the presence of any side effects following their initial study day. If female, they will again be administered a urine pregnancy test to confirm the absence of pregnancy. The remainder of the procedure will be identical to day 1.

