## 12 Statistical considerations

#### 12.1 Power analysis

Power analysis for error rates and reaction times is based on effect sizes from previous studies of the Emotional Go/NoGo task in subjects with schizophrenia and our preliminary data from a secondary analysis of a clinical trial of the alpha-7 nicotinic agonist GTS-21. With a sample size of 25 subjects, we will achieve 80% power at  $\Box$ lpha = 0.05 to detect a difference from 35% to 10% in the omission error between two experimental conditions within a subject (expected correlation of 0.60) and to detect an effect size of 0.6 in the mean reaction times between the control and intervention conditions within a person using paired t-test at alpha = 0.05. The dropout rate in a similar published acute crossover study of schizophrenia patients was ~15%. We thus anticipate needing to enroll 30 subjects to result in 25 completers for an appropriately powered study. We will match this group with a healthy control sample of similar size.

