#### 12.2 Data analysis plan

Omission error rate will be analyzed using non-linear mixed effects modeling of a binary outcome omission error (0/1), while reaction time will be analyzed with a linear mixed effects model. In both models, there will be a random effect for subject, a primary fixed independent predictor treatment condition (nicotine or placebo), an independent adjustment variable block valence (emotional vs. non-emotional task), and the interaction of the latter two predictors to examine whether the omission error rate or reaction time between two treatment conditions is moderated by the valence. Significance will be established at alpha = 0.05.

We expect nicotine will reduce error rates in control blocks consistent with previous reports of improved attention with acute dosing of transdermal nicotine. We expect to find an interaction between valence and treatment such that performance improves with nicotine to a significantly greater extent in negative valence blocks. We further expect this increase to be more prominent in individuals with schizophrenia than in healthy controls. We expect salivary nicotine concentration, which is proportional to serum nicotine, will correlate with improvement in response inhibition. Based on previous findings in the Emotional Go/NoGo task, we do not expect to find an effect of antipsychotic exposure, as measured by chlorpromazine equivalents.

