#### 12.3 Inclusion of men and women

We do not expect significant difficulties in patient recruitment based on previous studies with similar patient populations conducted in the [name] Lab. Men and women will be included in this study. Unlike highly sexually dimorphic rodent aggression, multiple studies find no significant gender difference in physical aggression amongst inpatients with schizophrenia. Given these previous findings and the above power analysis, it is outside the scope or resources of this focused study to power sufficiently to include sex/gender as a formal variable in our experimental design. However, all efforts will be made to recruit similar numbers of men and women to the study, final reported data will be disaggregated by sex/gender, and *hypothesis-generating* comparative analyses will be performed that can be pursued in future, *hypothesis-testing* prospective studies. Previous studies of nicotine for cognition in schizophrenia enrolled men and women, but no differences in their response to drug were reported. The inclusion of drug plasma levels can mitigate pharmacokinetic-based differential responses between men and women, and will be done in the proposed study.

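### Task timing is chosen for a nicotine peak near two hours, but the rule sets only a latest start; a target with a window on both sides would be a cheap improvement

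*Combined protocol and SAP*

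**What the plan says.** All the timing rules are in Section 6.2 (Testing: days 1 and 2).

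- Rationale: "two hours post-patch application represents an approximate time of peak serum concentration in most subjects". The section adds that this agrees with earlier published protocols.
- Rule, first statement: "Subjects will begin the behavioral task accompanied by EEG monitoring *at the latest* 120 minutes after patch placement".
- Rule, restated: "up to two hours after nicotine or placebo patch placement, subjects will begin participation in an Emotional Go/NoGo task".
- Exposure check: a saliva sample for nicotine is taken when the task ends, about 12 minutes after it starts. The patch then comes off.
- Day 2, after the treatment switch, side-effect questions and pregnancy test: "The remainder of the procedure will be identical to day 1".

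For the gap between test days, the same section gives both a target and a floor: "Testing occurs on two days separated by approximately one week, but no sooner than 5 days apart".

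Section 12.2 expects that salivary nicotine "will correlate with improvement in response inhibition", but drug level is not a term in the mixed models described there. Section 12.3, on sex differences, says: "The inclusion of drug plasma levels can mitigate pharmacokinetic-based differential responses between men and women, and will be done in the proposed study".

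**The concern.** The rule does not match its reason. If exposure peaks at about 120 minutes and 120 minutes is also the last permitted start, every departure that the rule allows is towards an earlier time and a lower level. A start at 60 or 90 minutes complies with both statements of the rule. Visits may also come under scheduling pressure: Section 6.1 allows screening to be combined with the first test session for subjects with transport or work constraints.

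At stake is sensitivity. Lower exposure on the nicotine day would shrink the difference from placebo, and the sample size has little slack above 80% power. Measuring saliva afterwards describes a low exposure but does not raise it.

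**Working it through.** **1. The plan's own figure.** Inputs from Section 12.1: 25 completers, paired t-test, alpha 0.05, and an effect "to detect an effect size of 0.6 in the mean reaction times between the control and intervention conditions within a person". The plan does not say whether the test is one- or two-sided; two-sided is assumed here. Power = P(|T| > t(0.975, 24)), where T is noncentral t with 24 degrees of freedom and noncentrality dz × √25. With dz = 0.6 this is 0.6 × 5 = 3.0, giving 82.1%. The smallest n reaching 80% is 24 (80.4%). Enrolment is 25 / 0.85 = 29.4, rounded up to 30. The plan's figures reproduce.

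**2. Permitted start times.** As written, the task may start at any time from 0 to 120 minutes and ends about 12 minutes later. Only the upper end matches the stated peak.

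**3. How much slack there is.** For 25 completers, 80% power needs dz of about 0.584, so the effect must stay at 0.584 / 0.6 = 0.973 of its planned size.

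**4. Illustration.** The documents give no concentration-time curve, so three things are assumed: the effect of 0.6 applies at 120-minute exposure, the effect is proportional to exposure, and the start times are as listed. Let f(t) be exposure relative to 120 minutes, and dz = 0.6 × f. The only curve tried that has its maximum at two hours, as Section 6.2 states, is f(t) = (t/120) × exp(1 − t/120). Even spreads use the mean of f over the interval.

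| Starts | f | dz | Power | Loss (points) |
|---|---|---|---|---|
| All at 120 min | 1 | 0.600 | 82.1% | – |
| Even, 90–120 min | 0.988 | 0.593 | 81.2% | 0.9 |
| All at 90 min | 0.75 × e^0.25 = 0.963 | 0.578 | 79.2% | 2.9 |
| Even, 60–120 min | 0.946 | 0.568 | 77.7% | 4.4 |

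A simulation with individual start times agreed with the even-spread figures to within 0.4 points. On this curve, power drops below 80% only if all sessions start before about 94 minutes. The extreme case, every session at 60 minutes, has f = 0.5 × e^0.5 = 0.824, dz = 0.495 and power 66.0%.

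**5. Sensitivity to the curve.** With exponential rises, f(t) = (1 − 2^(−t/h)) / (1 − 2^(−120/h)) and half-time h of 20, 30 or 45 minutes, power is:

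- even over 90–120: 81.2, 79.8 and 78.0%
- all at 90: 79.8, 76.6 and 72.7%
- even over 60–120: 79.1, 75.7 and 71.6%

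A straight-line rise, f = t/120, gives 71.2, 57.9 and 57.9% for the same three patterns. It is a pessimistic bound that fits poorly with a peak near two hours.

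**6. A window of 105 to 135 minutes.** On the peaked curve, f(105) = 0.875 × e^0.125 = 0.9915 and f(135) = 1.125 × e^(−0.125) = 0.9928. Power is 81.4% if every session starts at the lower limit and 81.5% if every session starts at the upper. On the exponential curves, all starts at 105 minutes give 81.2, 79.9 and 78.2%. Clustering at the floor can therefore still cost something, which is why a stated target matters.

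Omission error is not scaled, because Section 12.1 gives no subject-level standard deviation. The treatment-by-valence interaction is not covered either.

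**The case against.** The other side has a good case.

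- Two hours is plainly the working target. It is named as the peak, tied to earlier protocols, and followed at once by a rule framed around 120 minutes. The ceiling may only be meant to stop overrun. This stands as a reading of intent, but the rule still sets no lower limit.
- Figure 1, cited for the session layout, is not shown and may carry a timing label. This stands, and the point rests on the written rule alone.
- The five-day floor between visits serves drug washout, a different purpose. True; it shows only that the section states a target and floor where the authors wanted one.
- Exposure is partly handled. Saliva measures delivered nicotine more directly than clock time does, and making day 2 the same as day 1 helps consistency between days. Both stand, but two early sessions would be consistent and both off-peak.
- The power figures rest on assumptions. Section 12.1 takes its effect sizes from an earlier Emotional Go/NoGo study and from trial data on a different nicotinic agonist, so 0.6 is not tied to a nicotine patch at 120 minutes. Section 12.2 expects a correlation with exposure, not proportionality. This stands in full.
- A floor could lengthen wear for subjects with discomfort. Section 8.1.1 reports mild nausea and lightheadedness after one hour in 5 of 8 non-smokers, though at 15 mg rather than 7 mg. This is a real cost, and the fix must respect it.

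A reader might infer that early starts are planned, or that the trial is shown to fall below 80% power. The documents support neither: no passage schedules early sessions, and no exposure curve or start-time distribution is given.

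**Conclusion.** The point holds as a low-severity design improvement. The rationale points to two hours, while the rule permits any start up to two hours, so a compliant session can run at lower exposure and may dilute the nicotine-placebo contrast.

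The size of any loss cannot be derived from the documents. On a curve peaking at 120 minutes, under the assumptions in step 4, it is about 1 to 4 points of reaction-time power for starts spread over the last 30 to 60 minutes before the ceiling. Slower-rising curves, or sessions clustered well before 90 minutes, would cost more, but nothing in the documents makes those cases likely.

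It would also be wrong to infer that the results would be invalid. Blinding, randomised order and the false-positive rate do not depend on when the task starts within this rule.

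**What to change.** In Section 6.2, replace the one-sided limit with a target of 120 minutes and a window on both sides, for example 120 plus or minus 15 minutes, with the investigator setting the final limits. Centre the window on the target. If 120 minutes were both target and hard ceiling, any small overrun would be a deviation and staff would tend to start early.

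- Use the same patch-to-task interval on both test days.
- Record the minutes from patch placement to task start at each session.
- Keep out-of-window sessions in the primary analysis and list them as deviations.
- Leave the right to patch removal for discomfort (Section 8.2.1) unchanged.
- A treatment-by-interval sensitivity term is optional, since Section 12.2 already looks at salivary nicotine.

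The cost is a sentence of protocol wording and one recorded time per session, with slightly less scheduling flexibility and, for some subjects, somewhat longer patch wear. The sample size (25 completers, 30 enrolled), endpoints and primary models do not change.

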## 2 Rationale and specific aims

This human laboratory study seeks to test the hypothesis that activation of nicotinic acetylcholine receptors (nAChRs) in the brain will reduce impulsive behavior in response to negative emotional cues as compared to neutral emotional cues. Because impulsive action during negative mood states is strongly correlated with impulsive aggression in both healthy individuals and individuals with schizophrenia (discussed below), our overarching, long-term goal is to determine whether nAChRs in general as well as specific nAChR subclasses might represent novel treatment targets to reduce impulsive aggressive behavior, a significant public health problem.

Nicotinic acetylcholine receptors are a large family of excitatory, pentameric, ionotropic, ligand-gated ion channels located throughout the brain and the remainder of the body. Their endogenous ligand is acetylcholine, yet this family is defined by their common activation by nicotine. Interestingly, anti-aggressive, or "serenic" effects of nicotine have been demonstrated across a number of animal models, including mice, rats, and non-human primates, and multiple human laboratory studies demonstrate an anti-aggressive effect of nicotine in humans. As detailed in section 3.1, our laboratory has also demonstrated that acute administration of nicotine at relatively low doses results in reduction of aggressive behaviors in mouse models. Because nicotine is active at all nAChRs, we explored this mechanism further and found that hippocampal alpha-7 nAChRs were both necessary and sufficient for nicotine's serenic effect. Consistent with these findings, there is substantial evidence in humans that reduction of alpha-7 nAChR signaling enhances aggressive behavior, including in individuals with 15q13.3

microdeletion syndrome, a genetic disorder resulting from the deletion of the region of chromosome 15 containing the gene coding for alpha-7 nAChRs. We have also translated these findings into human clinical populations. We recently demonstrated the safety and efficacy of transdermal nicotine to reduce aggression and irritability in young adults with autism spectrum disorder, described in section 3.2. This work, along with other previous case studies in humans, supports targeting nAChRs using transdermal nicotine to reduce aggressive behaviors.

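### The planned treatment-by-'block valence' interaction is a treatment-by-block-type interaction and cannot be attributed specifically to negative emotion

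*Combined protocol and SAP*

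**What the plan says.** Section 2 gives the hypothesis: activating nicotinic receptors "will reduce impulsive behavior in response to negative emotional cues as compared to neutral emotional cues".

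Section 6.2 describes the task as "performed in 5 blocks of 32 trials, with 3 emotional blocks with angry/fearful/sad/disgust faces and 2 non-emotional blocks". The example rule for one block type is "Emotional blocks: go-angry/nogo-fear or go-fear/nogo-angry", and for the other "Non-emotional blocks: go-male/nogo-female or go-female/nogo-male". The Figure 2 caption adds an angry-versus-sad example, again one negative emotion against another. On stimuli, the section says "Fearful, sad, angry, and disgust faces (negative valence) and neutral faces will be taken from" a public image bank. It does not say which block type uses the neutral faces.

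Section 12.2 fits mixed models for omission error (binary) and reaction time, with treatment as the primary predictor, "an independent adjustment variable block valence (emotional vs. non-emotional task"), and the product of the two. The expected result is that "performance improves with nicotine to a significantly greater extent in negative valence blocks". The same section expects nicotine to lower error rates in control blocks as well, through better attention. No model term, sensitivity analysis or stated limitation separates the decision rule from the valence of the faces.

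**The concern.** In the pairings described, the emotional and non-emotional blocks differ in what the subject must decide, and not only in what the faces express. The valence term is coded by block, so it carries both differences. Nicotine could help more, or less, with one kind of discrimination than with the other for reasons unrelated to emotion. General attention is one such reason, and the plan names it. That would appear in the model as a treatment-by-valence interaction.

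The interaction is the only planned test that compares the nicotine effect across the two conditions named in the hypothesis. If it is significant and is read as an effect on emotional impulsivity, the trial claims something that the design does not isolate. A null result is equally ambiguous, since opposing valence and rule effects could cancel. The predicted larger effect in schizophrenia shares the problem, because section 3.2 cites a larger gain from nicotine in patients on an attention test.

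**Working it through.** **Inputs from the documents.** Section 6.2: 5 blocks of 32 trials, so 5 × 32 = 160 per session, of which 3 × 32 = 96 are emotional and 2 × 32 = 64 non-emotional; half are go trials. Section 12.1: "With a sample size of 25 subjects, we will achieve 80% power at" alpha 0.05 for a paired t-test with effect size 0.6; dropout about 15%; 30 enrolled. Two-sided testing is assumed, because the plan does not state sidedness.

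**Step 1: the plan's own figure.** Paired t-test power from the noncentral t distribution, with noncentrality d√n = 0.6 × √25 = 3.0 on 24 degrees of freedom, is 82.1%. The smallest n that reaches 80% is 24 (80.4%). Enrolment is 25/(1 − 0.15) = 29.4, rounded up to 30. The reaction-time sample size is reproduced. It concerns the treatment contrast; no effect size or SD is given for the interaction.

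**Step 2: what the interaction estimates.** Assume that every block follows the pairings described and that the gender blocks show neutral faces. Write the fixed effects as intercept, treatment T, valence V, T×V, rule R, T×R. In every block V = R, so T×V = T×R.

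| Design | Columns | Rank |
|---|---|---|
| As described | 6 | 4 |
| Rule and face valence crossed | 6 | 6 |
| One rule for both face types (no R terms) | 4 | 4 |

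In the first row only the sum of the T×V and T×R effects is estimable. More subjects do not change the rank.

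**Step 3: consequence for the test.** This is a t-test on each subject's interaction contrast, n = 25, two-sided 0.05. The standardised effects are assumptions, as the documents give none.

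| True valence interaction | True rule interaction | Rejection rate |
|---|---|---|
| 0 | 0.3 | 30% |
| 0 | 0.6 | 82% |
| 0.6 | 0 | 82% |
| 0.6 | −0.6 | 5% |

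The second and third rows cannot be told apart from the data.

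**Step 4: how large a spurious interaction could be.** Assume no emotion-specific action. Let ROR be the nicotine-versus-placebo odds ratio for an omission error under the emotion rule divided by that under the gender rule. ROR below 1 is the direction the plan predicts. All error rates are assumed.

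- *Uniform 30% relative reduction, 20% → 14% and 8% → 5.6%.* Odds ratios are (0.14/0.86)/(0.20/0.80) = 0.651 and (0.056/0.944)/(0.08/0.92) = 0.682. ROR = 0.651/0.682 = 0.95.
- *Gender rule at a floor, 20% → 14% and 5% → 5%.* ROR = 0.651/1 = 0.65.
- *Discriminability d′ raised by 15% under both rules, miss rate Φ(−d′/2).* d′ of 1.5 → 1.725 gives 22.7% → 19.4%, odds ratio 0.822. d′ of 3.0 → 3.45 gives 6.7% → 4.2%, odds ratio 0.616. ROR = 0.822/0.616 = 1.33.

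So the bias can be negligible, in the predicted direction, or against it.

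**The case against.** **The documents do not establish complete aliasing.** A reader might infer that valence and rule change together in every block. The pairings are offered as examples, the figure images are missing from the text available, and the neutral faces are not assigned to a block type. This stands, and the point is limited to the pairings described. It does not rescue the planned term. If the gender blocks used negative faces throughout, the contrast would be one of rule alone; if they used mixed faces, coding by block would still not separate rule from valence.

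**The headline arithmetic is scale-dependent.** A uniform 30% reduction gives falls of 6.0 and 2.4 points, and a reader might take the 3.6-point gap as a false valence effect. Section 12.2 models a binary outcome, presumably on the odds scale, where the same scenario gives 0.95. The 0.65 case requires no nicotine benefit in control blocks, contrary to what section 12.2 expects, and 1.33 runs against the predicted direction. Nothing in the documents shows that the emotion rule is harder. All of this stands: no particular size of bias is demonstrated.

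**Treatment is the primary predictor.** Section 12.2 gives it that role, calls valence an adjustment variable, and section 12.1 powers only the treatment contrast. This stands too. It would be wrong to infer that the main treatment comparison is compromised. But section 2 states the hypothesis as negative versus neutral, and that statement relies on the interaction.

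**The task follows a published procedure.** Keeping the layout preserves comparability with the study used for the power analysis, which is a good reason not to change the task. It does not make the two factors separable.

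**Conclusion.** The inference stated in section 12.2 is wrong as written: on the blocks described, the design cannot deliver an interaction specific to negative valence. What it estimates is whether the nicotine effect differs between an emotion-discrimination block and a gender-discrimination block. A real emotional effect may be present; it cannot be distinguished from an effect of the type or difficulty of the discrimination.

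The conclusion rests on the described pairings holding for all blocks and on the block-level coding. It does not depend on the assumed error rates, which show only that a spurious interaction could go either way or be close to nil. Treatment effects overall and within each block type remain interpretable. The documents do not support the stronger readings, that the trial's treatment comparison is invalid or that the task must be redesigned.

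**What to change.** In section 12.2:

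1. Name the factor *block type (emotion rule versus gender rule)* in place of block valence.
2. Report the treatment effect within each block type, for omission error and reaction time.
3. State that a significant treatment-by-block-type interaction will not, on its own, be reported as specific to negative valence.

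This is wording only, adds no trials or subjects, and can be made after data collection has begun. The downside is a narrower claim.

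A change to the stimulus list should not be required. Applying the gender rule to negative faces in half of the 64 non-emotional trials and to neutral faces in the other half would separate the factors within one rule, but it leaves 32 trials per face type, of which 16 are go trials. For 25 completers that is 16 × 25 = 400 go trials per cell. With an assumed 8% omission rate in all four cells and trials treated as independent, the standard error of the log ratio is √(4/(400 × 0.08 × 0.92)) = 0.369. Power for a ratio of 0.65 is then Φ(0.431/0.369 − 1.96), about 21%. The change would also alter the control condition and depart from the published layout. At most it is an optional exploratory check.
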